18 REGULATORY ISSUES

18.1 Ethics and Good Clinical Practice

This study must be carried out in compliance with the protocol. These procedures are designed to ensure adherence to Good Clinical Practice, as described in the following documents:

- 1. ICH Harmonized Tripartite Guidelines for Good Clinical Practice 1996.
- 2. US 21 Code of Federal Regulations dealing with clinical studies (including parts 50 and 56 concerning informed consent and IRB regulations).
- 3. US 21 Code of Federal Regulations Part 312, Food and Drug Administration Investigational New Drug Application

The investigator agrees to adhere to the instructions and procedures described in the protocol and thereby to adhere to the principles of Good Clinical Practice that it conforms to.

18.2 Institutional Review Board/Independent Ethics Committee

Before implementing this study, the protocol, the proposed informed consent form, and other information to participants must be reviewed by a properly constituted Institutional Review Board/Independent Ethics Committee (IRB/IEC). Documentation that the protocol and informed consent have been approved by the IRB/IEC must be provided before study initiation. Any amendments to the protocol, other than administrative ones, must be approved by this committee.

18.3 Informed Consent

The investigator or designee must explain to each participant (or legally authorized representative) the nature of the study, its purpose, the procedures involved, the expected duration, the potential risks and benefits involved and any discomfort it may entail. Each participant must be informed that participation in the study is voluntary and that he/she may withdraw from the study at any time and that withdrawal of consent will not affect his/her subsequent medical treatment or relationship with the treating physician.

The informed consent form(s) must be submitted by the investigator for IRB/IEC approval.

18.4 Subject Withdrawal

Subjects may withdraw consent at any time for any reason or be dropped from the trial at the discretion of the investigator should any untoward effect occur. In addition, a subject may be withdrawn by the investigator or the Sponsor if enrollment into the trial is inappropriate, the trial plan is violated, or for administrative and/or other safety reasons. Should the subject be withdrawn from the study, the reason for withdrawal must be documented in the CRF.

Subjects who discontinue/withdraw from treatment prior to completion of the treatment regimen should be encouraged to continue to be followed for all remaining study visits.

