11.2 Follow-up Evaluations

Study Visit 1 (2 weeks post-randomization +/- 7 days) – Virtual Visit

At this visit, two weeks after randomization, interim history, review of medications, adherence and tolerance assessment, and adverse event monitoring.

Study Visit 2 (4 weeks post-randomization +/- 7 days)

At this visit, four weeks after randomization, interim history, review of medications, physical examination, laboratory testing (white blood cells, hemoglobin, platelet count, sodium, potassium, BUN, creatinine, magnesium, AST/ALT, total and direct bilirubin, albumin, total protein, alkaline phosphatase, activated partial thromboplastin time, prothrombin time/INR, LDH, fibrinogen, d-dimer and Anti-Xa level), adherence and tolerance assessment, and adverse event monitoring. A biobank blood collection will be performed. Verification of listing status for transplant to ensure ongoing eligibility for study participation.

Study Visit 3 (6 weeks post-randomization +/- 7 days) – Virtual Visit

At this visit, six weeks after randomization, interim history, review of medications, adherence and tolerance assessment, and adverse event monitoring.

Study Visit 4 (8 weeks post-randomization +/- 7 days) – Virtual Visit with Labs

At this visit, eight weeks after randomization, interim history, review of medications, adherence and tolerance assessment, and adverse event monitoring. Remote lab testing will include white blood cells, hemoglobin, platelet count, sodium, potassium, BUN, creatinine, magnesium, AST/ALT, total and direct bilirubin, albumin, total protein, alkaline phosphatase, prothrombin time/INR, LDH.

Study Visit 5 (12 weeks post-randomization +/- 14 days)

At this visit, 12 weeks after randomization, interim history, review of medications, physical examination, laboratory testing (white blood cells, hemoglobin, platelet count, sodium, potassium, BUN, creatinine, magnesium, AST/ALT, total and direct bilirubin, albumin, total protein, alkaline phosphatase, activated partial thromboplastin time, prothrombin time/INR, LDH, fibrinogen, d-dimer and Anti-Xa level), adherence and tolerance assessment, and adverse event monitoring. A biobank blood collection will be performed. Verification of listing status for transplant to ensure ongoing eligibility for study participation.

Study Visit 6 (18 weeks post-randomization +/- 14 days) – Virtual Visit

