14.1.8 Subject Stopping Criteria and Drug Modification

For patients in the apixaban arm with a thromboembolic event (stroke, device thrombosis or arterial non-CNS thromboembolism), will be considered a study drug failure and converted to warfarin (withdrawn from active treatment). For patients experiencing a bleeding event, the aspirin will be discontinued. Only in patients with recurrent bleeding will the apixaban be discontinued (withdrawn from active treatment) and warfarin initiated at an INR goal of 1.5 to 2.0. Patients will continue to be followed per the study schedule through study completion.

For apixaban patients listed for transplant, who are upgraded to a status 1-3, the apixaban will be discontinued and the patient converted to warfarin. These patients will be followed until transplant or study completion. Each apixaban patient who does not complete the 6-month study duration will be replaced to ensure 20 patients are in the apixaban arm with complete follow-up.

For patients in the warfarin arm with a thromboembolic event, will be managed with a higher INR goal of 2.5 to 3.0. For patients experiencing a bleeding event, the aspirin will be discontinued. Only in patients with recurrent bleeding will the INR goal range be reduced to 1.5 to 2.0. For patients with a 3rd bleeding event, warfarin will be stopped, and the patient will be withdrawn from treatment and the patient followed according to the study protocol.

Any AE events occurring up to 72 hours after the study drug is discontinued will be considered a treatment-emergent adverse event.

All SAEs, except for those anticipated events listed above, occurring from signed informed consent through study completion will be captured on the AE eCRF. Unless exempted as described above, all SAEs, whether or not deemed drug-related or expected, must be reported to the IRB by the investigator or qualified designee within 24 hours of first becoming aware of the event. For this study, all-cause deaths will be reported on the AE eCRF. The investigator or qualified designee will enter the required information regarding the SAE into the appropriate module of the eCRF. If the eCRF system is temporarily unavailable, the event, including the investigator-determined causality to study drug should be reported via the back-up paper AE form. Upon return of the availability of the electronic data capture (EDC) system, the SAE information must be entered into the eCRF.

Follow-up

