15 STATISTICAL METHODS AND DATA ANALYSIS

15.1 General Design Issues

All planned analyses will be prospectively defined for this study and approved by the CC. The statistical analysis plan (SAP) will contain detailed information regarding the data analysis. The SAP will be finalized prior to trial completion and will be approved by the coordinating center statistical team.

Analysis of the DOAC LVAD Study will be based on intention to treat (ITT). That is, participants will be analyzed (and endpoints attributed) according to the treatment strategy to which participants are randomized, regardless of subsequent additional post-randomization treatment and medical care. The ITT population will correspond to all randomized participants. The primary and secondary analyses will follow the ITT principle.

Baseline demographic and clinical variables will be summarized for each randomized arm of the study. Descriptive summaries of the distribution of continuous variables will be presented in terms of percentiles (e.g., median, 25th and 75th percentiles) along with means and standard deviations. Categorical variables will be summarized in terms of frequencies and percentages.

In addition, exploratory analyses will be performed to help explain and understand findings observed from the planned analyses. Statistical tests with a p-value <0.05 will be considered statistically significant, unless otherwise stated. Analyses will be performed using SAS software (SAS Institute, Inc, Cary, NC).

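### Section 18.4 allows removal from the trial itself, not only from treatment, after any untoward effect or plan violation, so endpoint follow-up can end selectively where Section 14.1.8 would continue it

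*Combined protocol and SAP*

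**What the plan says.** **Section 18.4 (Subject Withdrawal).** Apart from withdrawing consent, a subject may "be dropped from the trial at the discretion of the investigator should any untoward effect occur". The investigator or the sponsor may also withdraw a subject "if enrollment into the trial is inappropriate, the trial plan is violated, or for administrative and/or other safety reasons". The only sentence on retention reads "Subjects who discontinue/withdraw from treatment prior to completion of the treatment regimen should be encouraged to continue to be followed for all remaining study visits". It applies to withdrawal from treatment, and it encourages follow-up without requiring it. The reason for withdrawal from the study must be recorded in the CRF.

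**Section 14.1.8 (Subject Stopping Criteria).** Apixaban patients with a thromboembolic event or recurrent bleeding are taken off active treatment, and "Patients will continue to be followed per the study schedule through study completion". A warfarin patient with a third bleed leaves treatment but is still followed. Apixaban patients upgraded to transplant status 1-3 are followed to transplant or study completion; upgraded warfarin patients are not mentioned. Apixaban patients who do not complete six months are replaced. Section 7.3 says warfarin patients are not replaced.

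**Section 15.1.** Analysis is by randomized arm, "regardless of subsequent additional post-randomization treatment and medical care", and the ITT population is everyone randomized.

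**Sections 15.3 and 15.4.** The primary analysis is a Cox model for time to the composite. The censoring list in 15.4 covers status upgrade, transplant, transfer of care, and decommissioning or explant. It does not mention withdrawal by the investigator or sponsor.

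**Section 11.2.** Several visits include "Verification of listing status for transplant to ensure ongoing eligibility for study participation".

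**The concern.** The two sections give different answers to one question: when something goes wrong for a patient, does endpoint collection continue? Section 14.1.8 says yes for the events it lists. Section 18.4 permits no, for any untoward effect, at the discretion of someone who knows the arm.

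An exit prompted by an emerging problem is not independent of the outcome. Censoring at that point treats the patient as having the same future risk as those who remain, when the reason for leaving suggests a higher one. If exits differ between arms, the comparison shifts. Analysing by ITT does not help, because it cannot use data that were never collected.

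Two design features raise the stakes:

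- **Replacement is one-sided.** An apixaban patient dropped early can be replaced by a new one; a warfarin patient cannot.
- **The enrollment-pause triggers in Section 17.2 are small absolute counts in the apixaban arm:** 2 thromboembolic events, 4 major bleeds, or 2 deaths from either cause. One uncollected event can keep the count below a trigger, even in a patient whose first primary event was already recorded.

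**Working it through.** The plan gives no event rate, dropout rate or margin, and Section 15.2 says the sample size was not statistically derived. There is no stated figure to reproduce. The check is therefore a comparison of the text, followed by an illustration of size.

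**Step 1: which events can be lost.**

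| Situation | Consequence for the data |
|---|---|
| A primary event itself prompts the exit | Already counted in a time-to-first-event analysis. Later deaths, secondary components and DSMB counts can be lost. |
| A TIA prompts the exit | Anticipated event (14.1.6), not a component in 12.1. A later first primary event can be lost. |
| An isolated LDH rise prompts the exit | Appendix B also requires an accompanying event or intervention for suspected device thrombosis, so this is not yet an endpoint. A later one can be lost. |
| A Type 2 bleed prompts the exit | Section 12.1 names bleeding without a grade; 15.3 describes the composite as major events, and Appendix B defines major as Types 3-5. On the 15.3 reading, a later first primary event can be lost. |
| Plan violation or administrative exit | Any later first primary event can be lost. |

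**Step 2: size in a 20-patient arm.** Inputs: about 40 patients randomized 1:1 (Sections 7.2 and 15.2), so 20 per arm and 1/20 = 5 percentage points per patient. Assumed: 6 of 20 apixaban patients would have a primary event, and 2 of those 6 are dropped before it.

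- Full follow-up: event-free = 14/20 = 70%.
- Both dropped before any other event: 18 at risk, 4 events observed, product-limit estimate 14/18 = 77.8%.
- Both dropped after the other four events: 16/20 = 80%.
- Error: about 8 to 10 points in favour of apixaban.

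**Step 3: range over the assumed risk p.** If d patients leave just before their event and before the other events, the observed event proportion is (20p − d)/(20 − d). The ratio assumes the same true p on warfarin.

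| p | d = 1 | d = 2 | Ratio to warfarin, d = 2 |
|---|---|---|---|
| 20% | 3/19 = 15.8% | 2/18 = 11.1% | 0.56 |
| 30% | 5/19 = 26.3% | 4/18 = 22.2% | 0.74 |
| 40% | 7/19 = 36.8% | 6/18 = 33.3% | 0.83 |

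**Step 4: effect on the hazard ratio.** An exponential simulation (200,000 patients, 24 weeks, true risk 20%, 30% or 40% and equal in both arms) dropped a fraction of apixaban patients with an impending event at 90% of the time to that event. With the true hazard ratio at 1.0, dropping 10%, 25% or 50% of them gave apparent ratios of about 0.90, 0.75 and 0.50 at all three risks.

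**Step 5: the opposite case.** The direction depends on who leaves. If the 2 dropped patients come from the 14 who would stay event-free, and leave at the outset, the estimate is 12/18 = 66.7%, slightly too unfavourable. Exits unrelated to outcome give no expected bias.

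**The case against.** The strongest reply is that 18.4 is permissive general wording, that the specific rules in 14.1.8 govern the events that matter, and that 18.4 encourages continued visits after treatment withdrawal. Exit reasons are documented, and Section 14.1.8 has investigators follow SAEs to resolution, stabilization, explanation or final follow-up. Section 15.2 calls this a pilot not designed for statistical significance, with each patient reviewed individually. All of this lowers the likely damage. It does not remove the gap: the retention sentence does not reach a patient removed from the trial, and SAE follow-up covers an event already reported, not a new one.

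Four stronger readings are tempting, and the documents do not support them.

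- **A first severe bleed leads to a lost primary event.** A reader might infer this because 14.1.8 says "Only in patients with recurrent bleeding will the apixaban be discontinued", which seems to leave 18.4 as the only way off the drug. But a severe bleed is already a primary event and counts once it occurs. The last sentence of 18.4 also contemplates leaving treatment without ending follow-up.
- **The ITT population is breached.** Section 18.4 removes nobody from it. What is lost is follow-up.
- **Section 11.2 is a second removal route.** It ties listing status to eligibility for participation but contains no instruction to remove anyone. The wording needs reconciling, no more.
- **The result will be 8 to 10 points too favourable.** That figure assumes both dropped patients were about to have an event. The documents give no exit or event rate.

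**Conclusion.** The point holds in a limited form. Section 18.4 permits the investigator or sponsor to end a patient's follow-up on grounds that can be related to outcome, in conflict with the separation of treatment and follow-up in 14.1.8, and no handling is stated for such exits. The exposure is to first primary events after a lesser or non-endpoint effect or a plan violation, and to later deaths, secondary components and DSMB trigger counts. Apixaban-only replacement makes it worse.

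The 70% against 78% to 80% illustration shows how sensitive a 20-patient arm is. It rests on an assumed event rate and an assumed adverse pattern of exits, and it is not a forecast. The conflict in the wording depends on neither assumption. It should be corrected, and correcting it changes no sample size.

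**What to change.** 1. **Section 18.4:** separate leaving study treatment from leaving the study. State that withdrawal by the investigator or sponsor for untoward effects, plan violations, ineligibility found later or administrative reasons does not end collection of vital status and primary-endpoint events. Collection continues to week 24, and to the week 28 contact, for all randomized patients in both arms unless consent is withdrawn or follow-up ends as in 14.1.8.
2. **Transplant listing:** reconcile the eligibility wording in 11.2 and the censoring at status upgrade in 15.4 with the follow-up rule in 14.1.8, and say what applies to upgraded warfarin patients. Otherwise, data collected after upgrade would still be censored.
3. **Treatment stopping:** reconcile the discretion in 18.4 with the treatment-stopping wording in 14.1.8. Which clinical rule applies is for the sponsor and investigators; this review does not choose one.
4. **Analysis:** state how any remaining early exits enter the primary analysis, add a sensitivity analysis, and report exits by arm, time and reason.

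The cost is protocol wording and a few extra contacts for patients off study drug. Five of the eight scheduled follow-up contacts in Appendix C (weeks 2, 6, 8, 18 and 28) are already virtual.

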18.5 Investigational New Drug (IND) Application

The investigator or designee will file for an investigational new drug (IND) with the Food and Drug Administration (FDA) prior to initiation of the clinical trial. This will permit the FDA to determine that apixaban is reasonably safe for initial use in LVAD patients. This is an investigator IND for an approved product (apixaban), that will be used in a new patient population (LVAD patients). This IND will not be used to change the labeling of apixaban.

19 APPENDICES

19.1 Appendix A – Warfarin Dosing Protocol

Inova Fairfax Medical Center Inpatient Warfarin New Start Guideline (Days 1-2) If warfarin was intentionally held on admission for reason other than supratherapeutic INR (e.g., need for surgery), resume home dose on days 1-2 and then and then utilize Guideline for Days 3-7 thereafter

Step 1: Assess for patient characteristics that may impact warfarin sensitivity							
Factors that increase Baseline INR 70 years of Decompensa Significant live Weight < 60 h Malabsorptio Chronic diarr Malnourished	warfarin sensitivity: > 1.5 f age ted HF er disease {g n syndrome hea	Factors that decrease warfarin sensitivity: • < 60 years of age • BMI > 30					
Step 2: Evaluate for	severe and major dr	ug-drug interactions					
Severe drug-drug inte SMX/TMP Metronidazol		Major drug-drug interactions:					
	arfarin initiation dos						
Warfarin 2.5 mg	Warfarin 4 mg	Warfarin 5 mg	Warfarin 7.5 mg				
Any factor that increases warfarin sensitivity	No factor that increases warfarin sensitivity	No factor that increases warfarin sensitivity	No factor that increases warfarin sensitivity				
OR	AND	AND	AND				
Any severe drug- drug interaction	No severe drug- drug interactions	No severe or major drug-drug interactions	No severe or major drug-drug interactions				
OR	AND		AND				
≥ 2 Major drug-drug interactions	1 major drug-drug interaction		BOTH factors that decrease warfarin sensitivity				
	Recommended starting dose is intended for days 1 and 2 of warfarin therapy. Subsequently see "IFMC Inpatient Warfarin New Start Guideline (D3-D7)"						

Inova Fairfax Medical Center Warfarin New Start Guideline (Days 3 – 7)

Day	INR Goal 2.0 – 2.5	Instruction In additional to instructions below, consideration should be given to the rate of INR increase/decrease, perceived warfarin responsiveness/sensitivity, initiation/discontinuation of interacting medications, and clinical status of the patient. The INR should increase 0.1 − 0.3 per day until steady state is achieved at approximately one week. If INR increases ≥ 0.4 per day, decrease dose by 25 − 50% If INR increases ≥ 1 per day, HOLD a dose				
1 – 2		See "IFMC Inpatient Warfarin New Start Guideline (Days 1 – 2)"				
	< 1.5	1 – 2x initial dose				
3	1.5 – 1.9	Continue initial dose				
3	2.0 – 2.5	0.25 – 0.5x initial dose				
	≥ 2.6	HOLD				
	< 1.5	1.5 – 2x initial dose				
	1.5 – 1.9	1 – 1.5x initial dose				
4	2.0 – 2.5	Continue last dose				
	2.6 – 2.9	0.75x last dose				
	≥ 3.0	0.25x last dose or HOLD				
	< 1.5	2x initial dose				
	1.5 – 1.9	1 – 2x initial dose				
5	2.0 – 2.5	Continue last dose				
	2.6 – 2.9	0.5x last dose				
	≥ 3.0	0.25x last dose or HOLD				
	< 1.5	2 – 3x initial dose				
	1.5 – 1.9	1.5 – 2x initial dose				
6	2.0 – 2.5	Continue last dose				
	2.6 – 2.9	0.75x last dose				
	≥ 3.0	0.25x last dose or HOLD				
	< 2.0	2 – 3x initial dose				
7	2.0 – 2.5	Continue last dose				
,	2.6 – 2.9	0.8 – 0.9x last dose				
	≥ 3.0	0.75x last dose or HOLD				
See "IFMC Inpatient Warfarin Maintenance Protocol" for dosing after 7 days						

19.2 Appendix B - Adverse Event Definitions

- Arrhythmias: Any documented arrhythmia that results in clinical compromise, or requires hospitalization or treatment. Arrhythmias will be further classified as sustained ventricular arrhythmia or sustained supraventricular arrhythmia
- Arterial non-CNS thromboembolism: Acute systemic arterial perfusion deficit in any non-cerebrovascular organ system due to thromboembolism confirmed by 1 or more of the following: 1) standard clinical and laboratory testing, 2) operative findings, 3) autopsy findings
- Bleeding: the location/source of the bleed will be recorded and subsequently categorized as follows; CNS bleeding will be captured under cerebrovascular event/stroke
 - Type 2: Any overt, actionable sign of hemorrhage that does not fit the criteria for Type 3, 4, or 5 but does meet at least one of the following criteria:
 - 1) requiring non-surgical, medical intervention by a healthcare professional
 - 2) leading to hospitalization or increased level of care; or
 - 3) prompting evaluation
 - Type 3a
 - Overt bleeding accompanied by hemoglobin drop of 3 to < 5 g/dL
 - Any transfusion with overt bleeding
 - o Type 3b
 - Overt bleeding plus hemoglobin drop 5 g/dL or greater
 - Cardiac tamponade
 - Bleeding requiring surgical intervention for control (excluding dental/nasal/skin/hemorrhoid)
 - Bleeding requiring intravenous vasoactive agents
 - Type 4: VAD implantation-related bleeding (includes concomitant cardiac or non-cardiac surgical procedure)
 - Reoperation after the closure of incision or incisions used to implant the VAD to control bleeding
 - ≥ 50 kg: ≥ 4U pRBC within any 48 hours during the first 7 days postimplant
 - < 50 kg: ≥ 20 cm³/kg pRBC within any 24 hours during the first 7 days post-implant
 - Chest tube output > 2 liters within 24 hours
 - Type 5a: Probably fatal bleeding; no autopsy or imaging confirmation but clinically suspicious
 - Type 5b: Definite fatal bleeding; overt bleeding or autopsy or imaging confirmation
 - o For all types of bleeding, the event will be classified as:
 - Patient-related (e.g., coagulopathy unrelated to surgical technique such as non-adherence with anticoagulation medication resulting in inappropriately high level of anticoagulation, hepatic failure)
 - Management-related (e.g., related to surgical technique, hypertension, bleeding in the setting of inappropriate levels of anticoagulation)
 - Pump-related (e.g., bleeding from the outflow graft, apical connector, or other internal components
- Major bleeding: Bleeding Types 3-5
- **Cerebrovascular event:** This refers to cerebrovascular accidents (stroke) of any cause (ischemic or hemorrhagic).
- Device Explant: This refers to LVAD explantation or LVAD decommissioning for myocardial recovery.
- Device Thrombosis: This refers to suspected or confirmed device thrombosis.
 - Suspected device thrombosis is a major device-related malfunction which clinical or device parameters suggest thrombus on the blood-contacting components of the pump, cannula, or grafts. Suspected device thrombosis will be defined as signs and symptoms to include at least 1 of the 3 following criteria:

- 1) Presence of major hemolysis by LDH or clinical evidence of hemolysis by hemoglobinuria
- 2) Presence of heart failure not explained by structural heart disease
- Abnormal pump parameters consistent with diminished pump output/pump efficiency/pump performance

And

- Suspected device thrombus will be accompanied by 1 or more of the following events or interventions:
 - 1) Death
 - 2) Stroke or TIA
 - 3) Arterial non-CNS embolism
 - 4) De-novo need for inotrope therapy
 - 5) Treatment with IV anticoagulation, IV thrombolytics, or IV antiplatelet therapy
 - 6) Pump replacement
 - 7) Pump explanation with or without exchange
 - 8) Pump deactivation without pump removal
 - 9) Operation to repair or replace any internal components of the circulatory support system
 - 10) Urgent transplant listing (immediate urgent listing for transplant)
- Confirmed device thrombosis is major device-related malfunction in which thrombus is confirmed within the blood-contacting surfaces of device inflow cannula or outflow conduit or grafts. This can be reported through direct visualization inspection or by incontrovertible contrast radiographic evidence or by the absence of an appropriate Doppler flow signal that results in or could potentially induce circulatory failure or result in thromboembolism
- **Gastrointestinal Bleeding:** This refers to bleeding from the gastrointestinal tract that is or is not identified.
- **Infection:** This refers to any infection requiring antibiotic or antifungal therapy.
- Transient Ischemic Attack: a transient neurologic deficit that may persist for up to 24 hours.
- **Unplanned hospitalization, ER visit or clinic visit:** This refers to any medical evaluation for an LVAD patient that is unplanned.
- **Aortic root thrombus:** thrombus located on the aortic valve or in the aortic cusp or aortic root which is visualized on echocardiography or CT imaging.

